#### **10.4 Definition of Baseline**

Baseline for Lp(a), LDL-C, apoB, OxPL-apo(a), OxPL-apoB, and other lipid measurements will be defined the pre-dose measurement on Day 1 or closest to Day 1, prior to administration of Study Drug. The baseline for other measurements is defined as the last non-missing assessment prior to the first dose of Study Drug.

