### 5.1 Inclusion Criteria

1. Must have given written informed consent (signed and dated) and any authorizations required by local law and be able to comply with all study requirements
2. Males or females aged  $\geq 18$  and  $\leq 80$  years old at the time of informed consent
3. Clinical diagnosis of CVD defined as documented coronary artery disease (CAD), stroke, or peripheral artery disease
4. Lp(a) plasma level  $\geq 60$  mg/dL
5. Must be on standard-of-care preventative therapy for other than elevated Lp(a) CVD risk factors
6. Patients on the following medications must be on a stable regimen for at least 4 weeks prior to Screening and expected to remain on a stable regimen through the end of the post-treatment follow-up period:
  - a. lipid lowering drugs (statins, ezetimibe, proprotein convertase subtilisin/kexin type 9 [PCSK9s] inhibitors, niacin, fibrates, fish oil or other products containing omega-3 fatty acids including OTC preparations)
  - b. antiplatelet drugs
  - c. testosterone, estrogens, progesterone, growth hormone or progestins

7. Females: must be non-pregnant and non-lactating and either:
  - a. surgically sterile (e.g., tubal occlusion, hysterectomy, bilateral salpingectomy, bilateral oophorectomy)
  - b. post-menopausal (defined as 12 months of spontaneous amenorrhea in females > 55 years of age or, in females ≤ 55 years, 12 months of spontaneous amenorrhea without an alternative medical cause and FSH levels in the postmenopausal range for the laboratory involved)
  - c. Abstinent\* or
  - d. if engaged in sexual relations of child-bearing potential, agree to use 2 highly effective contraceptive methods (refer to [Section 6.3.1](#)) from the time of signing the informed consent form until at least 16 weeks after the last dose of Study Drug (ISIS 681257 or placebo)

\* Abstinence is only acceptable as true abstinence, i.e., when this is in line with the preferred and usual lifestyle of the patient. Periodic abstinence (e.g., calendar, ovulation, symptothermal, post-ovulation methods), declaration of abstinence for the duration of a trial and withdrawal are not acceptable methods of contraception
8. Males must be surgically sterile or, if engaged in sexual relations with a female of child-bearing potential, the patient must be using an acceptable contraceptive method (refer to [Section 6.3.1](#)) from the time of signing the informed consent form until at least 16 weeks after the last dose of ISIS 681257

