## 6.2 Additional Study Assessments

### 6.2.1 Laboratory Assessments

Laboratory analyte samples will be collected throughout the study. A list of these analytes is contained in [Appendix B](#).

Routine blood chemistry and urine samples (excluding 24-hour urine collection) should be taken after fasting for at least 10 hours. Any confirmatory test, or test taken for safety reasons, may be taken at any time, irrespective of fasting status. During preparation for fasting samples, the patient can drink water and they should ensure that they consume sufficient water in order to not become dehydrated.

If tests are uninterpretable (e.g., due to clumping, hemolysis or quantity not sufficient) or missing, a repeat blood or urine specimen should be re-drawn as soon as possible (ideally within 1 week).

Hematology samples will be collected every 14 days. Each time a hematology lab is drawn and sent to the central laboratory for analysis, an additional sample must be collected in parallel and analyzed locally. In the event that both the central and local samples are unreportable (e.g., due to hemolyzed or clumped blood samples), patient dosing cannot continue until another sample is repeated and determined not to have met a platelet stopping rule.

If there is no reportable platelet count within 14 days of the last platelet count, the Investigator will contact the patient to hold dosing until a new platelet count is obtained and reviewed.

Blood and urine samples for renal function testing will also be collected every 14 days and sent to the central laboratory for analysis, per [Section 8.5.2](#). If there are no test results available within 14 days of the last set of results for parameters considered critical to patient safety, the Investigator will contact the patient to hold dosing until a new test set is obtained and reviewed.

Liver function testing will also be collected every 14 days and sent to the central laboratory for analysis for the first 3 months of the study treatment, and monthly thereafter during the Treatment Period per [Section 8.5.1](#).

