### **8.6 Stopping Rules**

For the purposes of stopping rules, Baseline is defined as the average of Day 1 pre-dose assessment and the last measurement prior to Day 1.

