### **10.2 Sample Size Considerations**

Based upon prior clinical trial experience with ISIS 681257, it is estimated that the standard deviation of the percent change in Lp(a) is approximately 20%. With 23 patients in each ISIS 681257 treatment group and 23 in placebo group there would be approximately 90% power to detect a 20% difference in percent change in Lp(a) levels between the ISIS 681257 treatment groups and placebo group at an alpha level of 0.05, assuming 30% reduction in the ISIS 681257 patients and 10% reduction in the placebo patients.

Based upon prior clinical trial experience with Ionis ASOs, assuming the incidence rate of platelet count below lower limit of normal (LLN) in placebo treated patients is 1.9%, in the ISIS 681257 treated patients is 3.8%, twice the incidence rate observed in placebo, with 45 patients in each ISIS 681257 treatment group, there would be approximately 80% power to detect at least 1 event.

Therefore, approximately 270 patients (54 patients per cohort, including 45 patients per cohort treated with ISIS 681257) will be randomized to ensure that both the safety and efficacy of ISIS 681257 will be adequately characterized in the study.

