#### **10.6.3.2 Analysis of Secondary Efficacy Endpoints**

- Percent change from baseline at the primary analysis time point in fasting LDL-C will be compared between each ISIS 681257 treatment groups and pooled placebo group using an ANCOVA model with baseline as covariate
- Proportion of patients who achieve  $\leq 50$  mg/dL in fasting Lp(a) at the primary analysis time point will be compared between each ISIS 681257 treatment group and pooled placebo group using a logistic regression model with Baseline Lp(a) as a covariate. Proportion of patients who achieve  $\leq 30$  mg/dL in fasting Lp(a) at the primary analysis time point will be analyzed similarly
- Percent change from baseline at the primary analysis time point in fasting apoB, OxPL-apo(a) and OxPL-apoB will be compared between ISIS 681257 treatment groups and pooled placebo group using an ANCOVA model with baseline as covariate

All analyses of secondary endpoints will be performed on the FAS as primary and PPS as supportive.

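### LDL-C and apoB are measured at Screening and Day 1 but only one value serves as baseline; averaging both would cheaply gain some precision

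*Protocol*

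**What the plan says.** All references are to the protocol, Amendment 4.

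- **Baseline.** Section 10.4 states that baseline for Lp(a), LDL-C, apoB, the two oxidized-phospholipid measures and other lipids "will be defined the pre-dose measurement on Day 1 or closest to Day 1, prior to administration of Study Drug". That is one value per patient.
- **Schedule.** In Appendix A, both schedules (weekly and every-2-week; every-4-week) mark the lipid panel at Screening and again at Day 1. Appendix B lists LDL-C and apoB in that panel. Screening runs from Day -28 to Day -1.
- **Comparable conditions.** Section 5.1, criterion 6: "Patients on the following medications must be on a stable regimen for at least 4 weeks prior to Screening"; lipid-lowering drugs head the list. Section 6.2.1 says that routine blood chemistry "should be taken after fasting for at least 10 hours".
- **Analysis.** Section 10.6.3.2 takes "Percent change from baseline at the primary analysis time point in fasting LDL-C" and compares each active group with pooled placebo by ANCOVA with baseline as covariate; apoB is handled in the same way.
- **Entry selection.** Section 5.1 sets a threshold on Lp(a) (60 mg/dL or above). Sections 5.1 and 5.2 set none on LDL-C or apoB.
- **Averaging elsewhere.** For stopping rules (Section 8.6), "Baseline is defined as the average of Day 1 pre-dose assessment and the last measurement prior to Day 1". Section 8.5 uses the same idea for safety monitoring.

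**The concern.** In the planned model the Day 1 draw is both the denominator of the percent change and the covariate. Visit-to-visit noise in that draw enters the outcome, and it also weakens the covariate's ability to explain the outcome. A second draw under comparable conditions is already scheduled, so the noise could be reduced without another sample.

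Precision in the secondary lipid comparisons is at stake. LDL-C and apoB are named in the secondary objectives and compared cohort by cohort (45 active against 45 pooled placebo), but the sample size was set on Lp(a) and on platelet events. Nothing in the plan fixes how small an LDL-C or apoB difference the trial can resolve.

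**Working it through.** **1. The plan's own efficacy figure.** Section 10.2 gives SD 20, difference 20, 23 against 23, "at an alpha level of 0.05"; Section 10.6 makes tests two-sided. The standard error is 20 × √(2/23) = 5.90 and the noncentrality is 20/5.90 = 3.39 on 44 degrees of freedom, giving 91.2% power against the stated approximately 90%. The figure reproduces, but it concerns Lp(a) only and neither supports nor contradicts this point.

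**2. Inputs the documents do not give.** There is no SD, visit-to-visit CV, within-patient correlation, expected effect or power for LDL-C or apoB. Every such value below is an assumption.

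**3. Formula.** Take a linear ANCOVA with unit variance at each visit. Let each pre-dose value correlate rf with Week 25/27, and let Screening and Day 1 correlate r12 with each other.

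- Residual variance, one baseline: 1 − rf²
- Residual variance, mean of two: 1 − 2rf²/(1 + r12)
- Relative saving: rf²(1 − r12) / [(1 + r12)(1 − rf²)]
- If all pairs of visits share one correlation r, the saving becomes r²/(1 + r)², with a limit of 25%.

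**4. Equal correlation at all visits.**

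- r = 0.5: 0.25/2.25 = 11.1%
- r = 0.7: 0.49/2.89 = 17.0%
- r = 0.9: 0.81/3.61 = 22.4%

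A saving of 12% needs r = 0.53, and 24% needs r = 0.96. Simulating percent-change ANCOVA on log-normal LDL-C, with r from 0.5 to 0.9, gives 16-23% (assumed CV 25%) and 20-24% (assumed CV 35%).

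**5. Screening and Day 1 agree better with each other than with a value about six months later.**

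- r12 = 0.8, rf = 0.7: 10.7%
- r12 = 0.8, rf = 0.6: 0.36 × 0.2 / (1.8 × 0.64) = 6.2%
- r12 = 0.9, rf = 0.7: 5.1%
- r12 = 0.9, rf = 0.6: 3.0%

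The first three, simulated as percent change at CV 35%, give 14%, 10% and 7%. Three percent is not a hard floor: r12 = 0.9 with rf = 0.5 gives 1.8%.

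**6. The same question in terms of visit noise.** A simulation of 45 against 45 with independent noise at each visit gives these ratios of residual variance (mean of two over single):

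- Visit CV 7%: 0.76 if the SD of individual change is 0, 0.88 if it is 10 points
- Visit CV 10%: 0.77 and 0.84
- Visit CV 12%: 0.77 and 0.83

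That is a saving of 12-24%. Raising the SD of individual change to 15-20 points reduces it to 5-13%. If half the baseline noise variance is shared by the two draws, it is 6-12% at SD 0-10 and 3-6% at SD 15-20.

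**7. What a saving is worth at 45 per arm.** Equivalent size is 45/(1 − saving); the standard error shrinks by 1 − √(1 − saving). The power figures start from an assumed 80%.

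- 3%: 46.4 per arm, standard error down 1.5%, power 81%
- 6%: 47.9 per arm, down 3.0%, power 82%
- 12%: 51.1 per arm, down 6.2%, power 85%
- 24%: 59.2 per arm, down 12.8%, power 90%

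For an assumed 8-point LDL-C difference at visit CV 10%, power moves from 81% to 90% (SD of individual change 0), 61% to 67% (SD 10), about 48% to 51% (SD 15) or 34% to 36% (SD 20).

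**The case against.** The strongest reply is that nothing here is wrong. A Day 1 pre-dose baseline used as a covariate is standard, and the randomised comparison is unbiased. No section contradicts it: the averaged baselines in Sections 8.5 and 8.6 serve safety monitoring and stopping rules, where a single noisy value could wrongly trigger action. This stands. Those sections show that averaging is workable in this trial, not that Section 10.4 is inconsistent.

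A reader might infer that the plan loses a fixed 12-24% of residual variance. The documents do not support that. The upper end needs almost no patient-to-patient variation in change over six months and independent noise at Screening and Day 1, although those draws may be only days apart. Other plausible settings bring the saving down to about 3%.

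A reader might also infer that the LDL-C and apoB comparisons are underpowered. The protocol states neither an expected effect nor a power for them, so no stated target is missed.

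Two smaller objections hold in part. The Screening value is not wholly discarded, because the wording allows the closest pre-dose value when Day 1 is unavailable. And Lp(a) carries apoB (Section 2.1.1), so selection on Screening Lp(a) could pass slightly into Screening apoB. Any such effect should be small and the same across randomised arms, so it does not undermine averaging.

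**Conclusion.** The point holds as an optional gain in efficiency. Section 10.4 fixes a single baseline where two comparable pre-dose lipid panels are already scheduled. Using both would reduce the residual variance for LDL-C and apoB by roughly 3-24%: about 12-24% when individual variation in change is small and visit noise is independent, about 3-13% when individual change is large or correlation falls by Week 25/27. The saving was positive in every setting computed, but its size rests on variability and correlation that the documents do not contain. It affects precision in secondary endpoints only. The primary Lp(a) analysis and the validity of the planned comparisons are untouched. Priority is low.

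**What to change.** In Section 10.4, define baseline for LDL-C, apoB and the other lipid-panel measures as the mean of the Screening and Day 1 pre-dose values, or the single value if one is missing. Alternatively, keep the Day 1 baseline and add the Screening value as a second ANCOVA covariate. That keeps one baseline rule, but for percent change it should recover less, because Day 1 noise stays in the denominator.

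Leave Lp(a) on Day 1: patients enter on a Screening Lp(a) threshold, so averaging that value in would bring regression to the mean into its baseline.

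The cost is one sentence, in the protocol or the SAP, settled before unblinding. No sample or visit is added. The drawbacks are a lipid baseline that reaches back up to 4 weeks and a rule that differs from the one for Lp(a).

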#### **10.5 Interim Analysis**

No interim efficacy analysis will be performed.

#### **10.6 Planned Methods of Analysis**

Summary tabulations will be provided for disposition, demographic, baseline, efficacy, and safety data as noted in the following sections. Hypothesis testing will be used for the primary efficacy endpoint and select secondary efficacy endpoints.

All eCRF data, lab data transfers, and any outcomes derived from the data will be provided in the patient data listings. Patient data listings will be presented for all patients enrolled into the study. Descriptive summary statistics including n, mean, median, standard deviation, standard error, interquartile range (25th percentile, 75th percentile), and range (minimum, maximum) for continuous variables, and counts and percentages for categorical variables will be used to summarize most data. Where appropriate, p-values will be reported. All statistical tests will be conducted using 2-sided tests with 5% Type I error rate unless otherwise stated.

##### ***10.6.1 Demographic and Baseline Characteristics***

Demographic and Baseline characteristics will be summarized using descriptive statistics by treatment group. The patient disposition will be summarized by treatment group. All patients enrolled will be included in a summary of patient disposition.

##### ***10.6.2 Safety Analysis***

###### ***10.6.2.1 Adverse Events***

Treatment duration and amount of Study Drug (ISIS 681257 or placebo) received will be summarized by treatment group. Patient incidence rates of all AEs will be tabulated by MedDRA system organ class, and by MedDRA preferred term. Narratives of treatment-emergent deaths, serious and significant AEs, including early withdrawals due to AEs, will also be provided.

All treatment-emergent AEs, all treatment-emergent AEs potentially related to Study Drug, all treatment-emergent serious AEs, and all treatment-emergent serious AEs potentially related to Study Drug (ISIS 681257 or placebo) will be summarized.

###### ***10.6.2.2 Clinical Laboratory Data***

Laboratory tests to ensure patient safety including chemistry panel, complete blood count (CBC) with differential, coagulation panel, complement, etc., will be summarized by study visits for each treatment group. These safety variables will also be presented as change and percent change from baseline over time after Study Drug (ISIS 681257 or placebo) administration, as

appropriate. In addition, the number of patients who experience abnormalities in clinical laboratory evaluations will be summarized by treatment group.

### **10.6.2.3 Vital Signs and Examinations**

Vital sign and ECG measures will be tabulated by treatment group.

### **10.6.3 Efficacy Analysis**

#### **10.6.3.1 Analysis of Primary Efficacy Endpoint**

The primary analysis of the primary endpoint will be the pairwise comparison of percent change from baseline to primary analysis time point in fasting Lp(a) between ISIS 681257 treatment groups and pooled placebo group in the FAS. The data will be analyzed using an analysis of covariance (ANCOVA) model with the Baseline Lp(a) as a covariate. Missing data may be handled by LOCF or multiple imputation methods ([Schafer 1997](#); [Schafer 1999](#)).

The primary efficacy analysis will take place after the last patient has completed the primary analysis time point and at least 50% of randomized patients have completed Week 52 visits, and the database has been locked,

The following sensitivity analyses will be conducted:

- The primary analysis will be repeated in the PPS
- The primary efficacy endpoint will be analyzed using a Wilcoxon Rank Sum test on both FAS and PPS, and the treatment effect will be estimated using Hodges-Lehmann estimator

Additional sensitivity analyses may be conducted as appropriate; the details of these analyses will be outlined in the SAP.

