### 3. EXPERIMENTAL PLAN

#### 3.1 Study Design

This is a Phase 2, multicenter, randomized, double-blind, placebo-controlled, dose-ranging study. Approximately 270 patients will be randomized in a 5:1 ratio (225 ISIS 681257 and 45 placebo) to receive ISIS 681257 or placebo. Study Drug (ISIS 681257 or placebo) will be administered SC every week, every 2 weeks (biweekly), or every 4 weeks, depending on cohort assignment, for up to 52 weekly doses, up to 26 every 2-week doses, or up to 13 every-4-week doses.

The primary analysis time point is at Week 25 for patients who received every 4-week dosing (Cohorts A-C) and at Week 27 for patients who received 2-week or weekly dosing (Cohorts D and E). For patients continuing treatment beyond the primary analysis time point additional supportive efficacy analysis (to evaluate whether the treatment effect is maintained) and safety analysis (for the purpose of dose(s) selection) will be repeated at the completion of Study Drug treatment.

The treatment portion of the study will be complete when the last enrolled patient reaches 6 months of exposure. All patients will then enter a 16-week post-treatment follow-up period.

Patients  $\geq 18$  and  $\leq 80$  years old with elevated plasma Lp(a) levels ( $\geq 60$  mg/dL ) and a clinical diagnosis of CVD are eligible for enrollment upon meeting the study specific eligibility criteria. Patients will be on standard-of-care preventative therapy for other than elevated Lp(a) CVD risk factors as per current guidelines.

Clinical diagnosis of CVD is defined as documented coronary artery disease (CAD), stroke, or peripheral artery disease (PAD). A diagnosis of CAD has to be documented by any of the following:

- Angiographic evidence of  $\geq 50\%$  stenosis of 1 or more major epicardial coronary arteries
- History of myocardial infarction documented by positive enzymes, and either symptoms of myocardial ischemia, or ECG changes ([Thygesen et al. 2012](#))
- History of coronary revascularization
- Evidence of cardiac ischemia on exercise testing, or imaging study

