#### **3.4.2 Treatment**

For each patient minimum treatment duration is 6 months and maximum of 52 weeks.

All patients enrolled will be randomized to a minimum of 6 months of treatment in 1 of 5 treatment cohorts. On completion of the 6 months, patients may continue treatment within the same randomized cohort until the last enrolled patient reaches 6 months of exposure (for continuing safety assessments), with a maximal exposure period of 12 months. When this milestone is met, all patients will then enter a 16-week post-treatment follow-up period.

Eligible patients will report to the Study Center for assessments at specified intervals throughout the 52-week treatment period as detailed in the Schedule of Procedures in [Appendix A](#). During the Treatment, Study Drug (ISIS 681257 or placebo) will be administered by SC injection once weekly, every 2 weeks, or every 4 weeks, depending on cohort assignment.

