## **4. PATIENT ENROLLMENT**

### **4.1 Screening**

Before patients may be enrolled into the study, the Sponsor or designee requires a copy of the Study Center's written independent ethics committee/institutional review board (IEC/IRB) approval of the protocol, informed consent form, and all other patient directed information and/or recruitment material.

Patients or their legally acceptable representatives must sign the consent form before any screening tests or assessments are performed. At the time of consent, the patient will be considered enrolled into the study and will be assigned a unique screening number before any study procedures, including screening procedures, are performed. The screening number and patient identification number must remain constant throughout the entire trial. In the event the patient is re-consented and re-screened the patient must be given a new screening number. Screening numbers and patient identification numbers, once assigned, will not be re-used.

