## Appendix A Schedule of Procedures – Weekly and Every 2 Week Dosing *Continued*

- j Blood samples to be collected after an overnight fast of at least 10 hours and preferably not more than 12 hours, unless tests are repeated for safety reasons.
- k If the platelet value, serum creatinine or liver enzyme tests are uninterpretable (e.g., due to clumping, hemolysis or quantity not sufficient) a repeat blood specimen should be re-drawn as soon as possible (ideally within 7 days). All platelet count results will be reviewed promptly (within 48 hours of receipt) by the Investigator as per [Section 6.2.1](#). Any case of a platelet count  $\leq 50,000/\text{mm}^3$  should be reported in an expedited fashion to the Sponsor.
- l Refer to [Appendix C](#) for PK Sampling schedule.
- m Women who are not surgically sterile or post-menopausal.
- n Serum and plasma samples will be collected and stored for follow-up exploration of laboratory findings and/or AEs (e.g., measurement of cytokine and/or chemokine levels, measurement of additional markers of kidney function, measurement of antibodies, etc.) in this or subsequent clinical studies of ISIS 681257.
- o Patients will continue treatment in the study until the last patient enrolled reaches 6 months of exposure, and 50% of the enrolled patients have received Study Drug for 52 weeks. When both of these milestones are met, all patients will then enter a 16-week post-treatment follow-up period.

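### Amendment 4 carries two end-of-treatment rules, and the 50%-at-Week-52 trigger for the primary analysis is assured only under the one in Appendix A

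*Protocol*

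**What the plan says.** All references are to the current text, Amendment 4.

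- **Main body.** Section 3.1 states: "The treatment portion of the study will be complete when the last enrolled patient reaches 6 months of exposure". The synopsis and Section 3.4 say the same. Section 3.4.2 lets treatment run past 6 months only up to that one event and then closes it: "When this milestone is met, all patients will then enter a 16-week post-treatment follow-up period". It also sets the limits for each patient: "For each patient minimum treatment duration is 6 months and maximum of 52 weeks".
- **Appendix A, footnote o** (in both dosing schedules). Treatment continues "until the last patient enrolled reaches 6 months of exposure, and 50% of the enrolled patients have received Study Drug for 52 weeks", and follow-up begins only when both conditions are met.
- **Section 10.6.3.1.** Once everyone is past the Week 25 or 27 assessment, the primary efficacy analysis still has to wait for a further condition: "at least 50% of randomized patients have completed Week 52 visits, and the database has been locked".

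The trigger counts randomized patients and footnote o counts enrolled patients. The schedules go from Week 49 to Week 53 (Day 365) and have no visit labelled Week 52.

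**The concern.** The analysis trigger depends on how many patients are treated for a full year, and that number is set by the rule that ends dosing. The main-body rule does not require anyone to reach 52 weeks. It moves every patient into follow-up once the last one has 6 months of exposure. If fewer than half have reached a year by then, the shortfall cannot be made up: treatment is over, and Section 4.3 does not replace withdrawals. The sponsor would then have to set the date of the primary analysis by a route that its Protocol does not provide. If footnote o governs instead, the trigger is sound, but patients can be dosed for longer than the synopsis and Section 3 say. Either way, two rules that can give different stopping dates stand in one version of the Protocol.

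**Working it through.** The Protocol states no figure for accrual time or for the share expected to reach a year, so there is none to reproduce.

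**Inputs**
- Minimum treatment 6 months, taken as 26 weeks; maximum 52 weeks (Section 3.4.2).
- About 270 randomized (Section 3.3), so the threshold is 0.5 × 270 = 135.
- Accrual time T and share d lost before 52 weeks: not in the Protocol. Both are assumptions and are varied below.

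**Main-body rule.** Count weeks from the first randomization. Dosing stops for all at T + 26. A patient randomized at week t can have at most T + 26 − t weeks, and 52 weeks requires t ≤ T − 26. With uniform accrual, the share reaching 52 weeks is (1 − d) × (T − 26)/T, or zero if T ≤ 26.

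| T (weeks) | Share, d = 0 | Patients of 270 | Share, d = 10% |
|---|---|---|---|
| 26 | 0% | 0 | 0% |
| 30 | 13% | 36 | 12% |
| 39 | 33% | 90 | 30% |
| 48 | 46% | 124 | 41% |
| 52 | 50% | 135 | 45% |
| 65 | 60% | 162 | 54% |

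Setting the share to 0.5 gives T = 26 / (1 − 0.5/(1 − d)): 52 weeks at d = 0, 54.9 at 5%, 58.5 at 10% and 69.3 at 20%.

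**Sensitivity to the accrual pattern (d = 0)**
- Linearly falling rate: share = 1 − (26/T)², so T = 26/√0.5 ≈ 37 weeks.
- Linearly rising rate: share = ((T − 26)/T)², so T = 26/(1 − √0.5) ≈ 89 weeks.
- Any pattern: if everyone is randomized within 26 weeks, essentially nobody has 52 weeks when dosing stops.

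**Footnote o.** Dosing stops at the later of T + 26 and the week when half have had 52 weeks, which is 52 + 0.5T/(1 − d) under uniform accrual. With d = 0:

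| T | Main-body end | Footnote o end | Difference | Last patient's exposure |
|---|---|---|---|---|
| 13 | 39 | 58.5 | 19.5 | 45.5 |
| 26 | 52 | 65 | 13 | 39 |
| 39 | 65 | 71.5 | 6.5 | 32.5 |
| 52 | 78 | 78 | 0 | 26 |

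So with uniform accrual and no dropout, the two rules coincide only if accrual lasts a year or more. For faster accrual they give different exposure, and only footnote o delivers the trigger. Even footnote o delivers it only if at least half stay on drug: each patient is capped at 52 weeks, so heavier dropout would leave the 50% unmet there too.

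**The case against.** The best reply is that footnote o and the trigger belong together. The superseded Amendment 3 text had neither the second milestone nor the 50% condition. Amendment 4 has both, so the main body may simply not have been updated, and Section 3.4.2 itself sends the reader to Appendix A for the schedule. This is a fair account of how the conflict arose. It does not resolve it: Section 3.4.2 speaks of one milestone, and nothing gives the footnote precedence.

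It is also fair that failure is conditional. Slow or front-loaded accrual could satisfy the trigger under either rule. And because Section 4.4 lets the sponsor decide when to unblind, an unmet trigger would call for an administrative correction.

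Three stronger readings are tempting, but the text does not support them.

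- **Screen failures could make footnote o impossible to satisfy.** Section 4.1 does say "At the time of consent, the patient will be considered enrolled into the study". But Section 3.1 places enrolment at Day 1, Section 3.4.2 has all enrolled patients randomized, and the footnote concerns exposure to drug. The inconsistent use of *enrolled* is a wording defect.
- **Sites could stop dosing at different times.** Both milestones are study-wide, so no site can determine either one alone.
- **Planned 12-month analyses would be lost.** Section 10.1 repeats the supportive analyses at completion of treatment, whenever that falls, and does not fix them at 12 months.

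The missing Week 52 visit is a labelling slip: the Week 53 visit on Day 365 is the only scheduled visit that fits.

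**Conclusion.** The point holds. Amendment 4 contains two incompatible end-of-treatment rules, and the trigger in Section 10.6.3.1 is assured only under footnote o, provided at least half of patients stay on drug for 52 weeks. Under the main-body rule it may never be met. With uniform accrual it fails if accrual takes less than 52 weeks, or less than 58.5 weeks with 10% dropout. The no-dropout threshold moves between about 37 and 89 weeks with the accrual pattern. These figures rest on assumed accrual and dropout and on 6 months being 26 weeks; the Protocol neither confirms nor excludes them.

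A reader might infer that the primary comparison itself is compromised. It is not: the endpoint is taken at Week 25 or 27, and its data, model and power do not depend on when dosing ends. What is affected is how long patients are treated and when the primary analysis may be run.

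**What to change.** 1. State one end-of-treatment rule and use it in the synopsis, Sections 3.1, 3.4 and 3.4.2, and footnote o of both schedules. Which rule stands is for the sponsor to decide.
2. Align the trigger in Section 10.6.3.1 with that rule and make it always reachable, for example by adding an alternative: or all patients have ended treatment. The 52-week cap guarantees that this event occurs. Deleting the 50% condition is not necessary and would discard a requirement that Amendment 4 added on purpose.
3. Use randomized patients as the denominator in both the trigger and footnote o.
4. Replace the reference to Week 52 visits with the scheduled Week 53 (Day 365) visit.

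The cost is protocol wording in the places listed, with no added patients or visits. Any difference in exposure follows from the sponsor's choice in step 1.
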